6.6 CONCOMITANT THERAPY

As a general rule, the only ophthalmic medications given to the patients are Study Products or AT, from the Screening Visit, Day 1 and until all the final study evaluations have been completed at Follow-Up Visit, Day 56 ±2, including the vehicle during the Run-In phase and the preservative free artificial tears (AT) provided by the Sponsor during the Follow-Up period.

The use (number of drops/day) of Study Products (Including vehicle) and AT (NIMP) will be clearly documented in the Patient Diary and eCRF.

6.6.1 Prohibited Concomitant Therapy

During the whole period of the participation to the trial (about 10 weeks) patients should not use ophthalmic steroids, ophthalmic immunomodulators such as cyclosporine A and lifitegrast, intranasal tear-secretagogues such as varenicline, ophthalmic topical anti-histamine, any derivatives of nerve growth factor, or any medications as part of another clinical trial. The use of artificial tears - lubricating eye drops not provided by the Sponsor is also forbidden. Patients should not use punctal plugs, contact lenses (including scleral lenses), moisture goggles, warm compresses or electro/magnetic stimulation devices on the eye, face or scalp. Before the study unmasking, a masked review of the concomitant medication taken by the patients during the study will be done in order to verify the presence of prohibited medication, their frequency and dosage in order to define the severity of the deviation.

6.6.2 Permitted Concomitant Therapy

During the Run-In period, no ocular topical treatment is allowed, except for Study Product vehicle ophthalmic solution, 3 times daily, provided by the Sponsor.

During the treatment period, only the study products (IMP or vehicle) will be allowed for topical ocular treatment.

During Follow-Up period, no topical treatment will be allowed except for commercially available preservative free AT, TID, provided by the Sponsor. Different administration frequencies of study products (including vehicle) and NIMP will be recorded and considered as protocol deviation.

During the entire duration of the study, any use of AT not provided by the sponsor will be recorded as concomitant medication and considered as protocol deviation.

Patients are encouraged to continue to take any systemic medications that they take as part of chronic disease management and not change their medical management as prescribed by their treating physician.

Patients are allowed to take over-the-counter painkillers, herbal products, vitamins and antacids. All systemic medications, over-the-counter painkillers, herbal products, vitamins, and antacids taken within 4 weeks prior to the start of and throughout the study will be clearly documented on the Concomitant Medications eCRF page.

Medication entries should be specific to drug product name and brand name (especially if containing a combination of active principles) and spelled correctly. The dose, unit, frequency, route of administration, start date, discontinuation date, and indication should also be recorded. For medications administered only one time, the frequency column may reflect "once."

6.6.3 Rescue Therapy

If a patient's ocular health worsens to an extent that is considered beyond reasonable risk to their vision or maintenance of an intact ocular surface, they will be asked to discontinue the treatment but to remain in the study for the assessment planned by the protocol until the expected end of study. An appropriate treatment could be given by their physician. There will be no predefined rescue therapy. It should be checked if the patient still meets all the criteria expected to remain in the study. All details should be recorded in the eCRF.

6.6.4 Other Therapy

No other therapy outside of what is outlined in permitted concomitant therapy is allowed during the course of this study.

7 DISCONTINUATION OF TRIAL INTERVENTION AND PARTICIPANT WITHDRAWAL FROM TRIAL

7.1 CRITERIA FOR DISCONTINUATION OF TRIAL INTERVENTION

7.1.1 Criteria for Permanent Discontinuation of Trial Intervention

Treatment discontinuation

Patients with tolerability issues, or worsening of symptoms and/or signs may be discontinued at any time during the study for the following reasons:

- 1) AEs that at Investigator discretion require treatment discontinuation.
- 2) Worsening of the clinical condition that requires treatment discontinuation per physician decision or ocular surgery.
- 3) Violation of study procedures that represent a protocol deviation deemed by the Investigator to require treatment discontinuation.
- 4) Withdrawal of patient's consent for any reason.
- 5) Patient is lost-to-follow-up notwithstanding all efforts to contact him/her (at least three documented attempts by phone and/or email).
- 6) Other (e.g., death, pregnancy, planned operation).

Except for items from #4 to #6 of the list reported above that imply also a study discontinuation, in case one of the events from #1 to #3 occurs, patients will be asked to complete the assessments planned by the protocol regardless the discontinuation of the study treatment and will receive preservative free AT, TID, provided by the Sponsor. In case of more than one reason, the main one will be reported in eCRF.

Study discontinuation

A premature discontinuation will occur when a patient who signed the ICF ceases participation in the study, regardless of circumstances, before the completion of the study protocol procedures.

Patients should be discontinued from the study for one of the following reasons:

- 1) Withdrawal of patient's consent for any reason.
- 2) AEs, protocol deviations and any other condition for which study procedures may compromise the safety and well-being of the patient, as per physician decision.
- 3) Patient is lost-to-follow-up notwithstanding all efforts to contact him/her (at least three documented attempts by phone and/or email).
- 4) Other (e.g., death, pregnancy, planned operation).

In all other situations, including cases where patients should be discontinued from study treatment, all efforts will be made to complete study visits and procedures as per protocol.

Before removal, each case should first be discussed with Dompé.

The reasons for premature discontinuation from the study will be reflected on the Study Termination Record of the eCRF. Unless the patient has withdrawn consent, patients who discontinue the treatment will not be withdrawn from the study by default, but it will be asked

to complete safety and efficacy assessments as per protocol.

The investigator will advise patients who prematurely discontinue any therapies or treatments for their condition and refer them for further treatment as appropriate.

7.1.2 Temporary Discontinuation or Interruption of Trial Intervention

Any patient that chooses to discontinue the trial will not be allowed to re-enter or be replaced. It will be documented whether or not each patient completed the clinical study. If, for a patient, study treatment or observations are discontinued, the primary reason for discontinuation will be recorded.

For any patient discontinuing the study following randomization, the Investigator will:

- Ask the patient to undergo, as far as possible, the following assessment as planned in this protocol. In case the patient withdraws from the study, the patient will be asked to undergo, as far as possible, a final medical visit (Early Exit Visit) to examine the patient's health conditions. This examination will verify that all values tested at screening have remained within a clinically acceptable range (i.e., not clinically significant changes compared to screening).
- Arrange for alternative medical care of the withdrawn patient, if necessary.
- Report in the eCRF date and time of the last dose administration, and date and primary reason for study discontinuation.
- Record in the eCRF any follow-up if the patient is withdrawn for an AE. AE's should be followed until resolution.

7.1.3 Rechallenge

Rechallenge is not permitted in this trial.

7.2 PARTICIPANT WITHDRAWAL FROM THE TRIAL

There are no criteria for temporary withdrawal from the trial. Any discontinuation or withdrawal will result in a permanent discontinuation. The criteria for permanent discontinuation from the trial are listed in § [7.1.1](#).

7.3 LOST TO FOLLOW-UP

Every effort will be made by the Clinical Trial Manager, CRO Project Team and Investigator or their designated staff, to reach patients who are lost to follow-up. Lost to follow-up is defined as patients who miss one or more study visits and are not reachable despite every reasonable attempt made at contacting them (at least three documented attempts by phone and/or email).

7.4 TRIAL STOPPING RULES

The Sponsor has the right to discontinue the study at any time for reasonable medical and/or administrative reasons. Reasons for discontinuation have to be documented appropriately. In

this event, no further patients will receive doses of the IMPs, and patients already having received a dose of IMP will not receive any further doses of the IMP but will undergo all safety assessments scheduled after the last dose of IMP, up to and including the end of study examination.

8 TRIAL ASSESSMENTS AND PROCEDURES

8.1 SCREENING/BASELINE

Site staff will conduct the following assessments in the order outlined below during each visit.

Visit 1 - Day -12±2: SCREENING

1. Informed Consent/HIPAA (only for USA).
2. Demographics, Ocular and Medical History, Previous and Concomitant Ocular and Systemic Medications and Conditions.
3. Pregnancy Test.
4. SANDE questionnaire.
5. Ophthalmic Examinations for each eye:
 - A. Best-Corrected Distance Visual Acuity (BCDVA) by ETDRS.
 - B. External Ocular Examination.
 - C. Schirmer-I test without anesthesia.
 - D. Slit Lamp Examination (SLE) of the anterior segment of the eye (cornea, conjunctiva, anterior chamber, iris, lids and lashes).
 - E. Assess bulbar redness (VBR 10).
 - F. Instill fluorescein and wait 30 seconds.
 - G. Assess fTBUT.
 - H. After 2-5 minutes from the time of fluorescein instillation, assess total corneal fluorescein staining score (NEI scale, score range 0-15).
 - I. Apply lissamine green.
 - J. Assess total conjunctival lissamine green staining score (NEI scale, score range 0-18).
6. Inclusion/Exclusion Criteria Screen the subject for protocol inclusion/exclusion criteria.
7. Dispense IMP (vehicle) eye drops to be instilled; the first drop will be instilled by the investigator or delegate and then the IMP (vehicle) will be instilled by the patient at home 3 times daily in both eyes for 12 days ±2.
8. Deliver instructions to patient.
9. Dispense the Patient Diary to record the administration of Study Product vehicle during the Run-In period (vehicle accountability), any new or changes in concomitant medications, any unusual medical condition.
10. Investigator will document the first administration of the Study Product (vehicle) in the patient's medical record following Visit 1 to confirm the first administration of the Study Product (vehicle).
11. AE monitoring and recording, as applicable.

RUN-IN (From Day -12±2 to Day 1):

Patients at home will proceed with the Run-In of 12 days ± 2 using the dispensed

Study Product vehicle eye drops (1 drop in both eyes 3 times a day). No other ophthalmic topical administrations are permitted.

Visit 2 - Day 1: BASELINE

Patients will be randomized if they continue to meet eligibility criteria at Visit 2/Baseline.

1. Concomitant Ocular and Systemic Medications and Conditions
2. AEs monitoring (recording and evaluation, as applicable)
3. Pregnancy Test
4. SANDE questionnaire
5. CCI
6. Ophthalmic Examinations in each eye:
 - A. Best-Corrected Distance Visual Acuity (BCDVA) by ETDRS
 - B. External Ocular Examination
 - C. Assess NIKBUT (at selected centers)
 - D. Schirmer-I test without anesthesia
 - E. Slit Lamp Examination (SLE) of the anterior segment of the eye (cornea, conjunctiva, anterior chamber, iris, lids and lashes)
 - F. Assess bulbar redness (VBR 10 scale)
 - G. Instill fluorescein and wait 30 seconds.
 - H. Assess fTBUT
 - I. After 2-5 minutes from the time of fluorescein instillation, assess total corneal fluorescein staining score (NEI scale, score range 0-15).
 - J. Apply lissamine green.
 - K. Assess total conjunctival lissamine green staining score (NEI scale, score range 0-18).
 - L. Perform CCI eyedrop CCI (only in patients with CCI)
 - M. Perform specular microscopy to assess corneal endothelial cells density (at selected sites that have a specular microscope already available).
 - N. Instill tropicamide eye drop solution 1% after 15 minutes/once pupils are adequately dilated perform fundus examination.
7. Inclusion/Exclusion: Patients must continue to meet the Screening/Enrollment Criteria. At the end of the Baseline Visit (Day 1), it will be determined if the subject qualifies for continued participation and treatment in the study.
8. Collect used/unused Study Product (vehicle) of the Run-In phase (to be checked by independent personnel)
9. Retrieve the Patient Diary for the run-in period.
10. Randomization
11. Study Product dispensing: eligible patients will be supplied with a bi-weekly kit of Study product (IMP or vehicle) after randomization, sufficient for 2 weeks of treatment per visit.
12. Deliver instruction to Subjects.
13. Dispense Patient Diary to record adherence to the administration of IMPs during the treatment period, any new or changes in concomitant medications, any unusual medical conditions.

14. AEs monitoring and reporting, as applicable.

8.2 TRIAL VISITS AND FOLLOW-UP ASSESSMENTS

Site staff will conduct the following assessments in the order outlined below during each visit.

Visit 3 - Week 2 (Day 13±1) STUDY PRODUCT PICK-UP VISIT

1. Concomitant Ocular and Systemic Medications Update.
2. AEs monitoring (recording and evaluation, as applicable).
3. Check the Patient Diary.
4. Collect Used/Unused Study Products (IMP or vehicle; to be checked by independent personnel).
5. Study Product Dispensing: Patients will be supplied with a biweekly kit of Study product (IMP or vehicle) sufficient for 2 weeks of treatment.

Visit 4 - Week 4 (Day 28±1): END OF TREATMENT VISIT or EARLY EXIT VISIT

1. Concomitant Ocular and Systemic Medications Update.
2. AEs monitoring (recording evaluation, as applicable).
3. Check the Patient Diary of the treatment period.
4. SANDE questionnaire.

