6.2 RATIONALE FOR TRIAL INTERVENTION

The trial tests two CCI concentrations of a new CCI rhNGF formulation (C mcg/mL or C mcg/mL) in patients with DED. This new formulation not only allows to CCI the concentration of rhNGF down to C mcg/mL, but also allows the storage at CCI °C of the ophthalmic solution containing the active principle, hence reducing patient burden with respect to storage and handling of IMP. The rationale for the selection of the two proposed CCI concentrations of rhNGF stems from both manufacturing and clinical rationales. Specifically, from a manufacturing standpoint, the development of the new CCI formulation opens the possibility to test a rhNGF concentration as CC as C mcg/mL, which will provide the opportunity to test the minimally effective dose in the target population. From a clinical standpoint, both the C and C mcg/mL proposed concentrations can reasonably be expected to be safe and effective in the target population based on previous clinical trial experience with different rhNGF concentrations. Specifically, starting from the first phase 2 clinical trial performed in Europe (REPARO, NGF0212) in patients with Neurotrophic Keratitis, both the C and C mcg/mL were proven safe and effective on corneal healing. The following clinical trials in DED also tested concentrations of rhNGF up to C mcg/mL. In the DED studies we observed efficacy on tear function but a suboptimal tolerability of the higher concentrations tested (for example, 48% patients reported eye pain in NGF0121 - PROTEGO-1, up to 63.5% in NGF0118, and 42% in NGF0216). Therefore, the new formulation of rhNGF was prepared to allow a CCI concentration with the goal of consequently CCI

CCI TEAEs for patients, while maintaining efficacy on DED signs. The C mcg/mL dose group has the potential to show clinical benefit since an earlier open-label study (NGF0213) in dry eye patients demonstrated that with doses as CC as C mcg/mL (obtained by on-site dilution of the C mcg/mL formulation) treatment (BID, 4 weeks), patients showed improvement in both SANDE and Schirmer scores up to 4 weeks post-completion of treatment (day 56). Hence, this trial aims to determine the safety and efficacy of 2 CCI concentrations of rhNGF in dry eye patients.

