5. CCI [REDACTED]
6. Ophthalmic Examinations:
 - A. Best-Corrected Distance Visual Acuity (BCDVA) by ETDRS.
 - B. External Ocular Examination.
 - C. Assess NIKBUT (at selected centers).
 - D. Schirmer-I test without anesthesia.
 - E. Slit Lamp Examination (SLE) of the anterior segment of the eye (cornea, conjunctiva, anterior chamber, iris, lids and lashes).
 - F. Assess bulbar redness (VBR 10 scale).
 - G. Instill fluorescein and wait 30 seconds.
 - H. Assess fTBUT.
 - I. After 2-5 minutes from the time of fluorescein instillation, assess total corneal fluorescein staining score (NEI, score range 0-15).
 - J. Apply lissamine green.
 - K. Assess total conjunctival lissamine green staining score ([NEI, score range 0-18).
 - L. Perform CCI [REDACTED] eyedrop CCI [REDACTED] (only in patients with CCI [REDACTED])
7. Collect used and unused Study Product (to be checked by independent personnel)
8. Retrieve Patient's Diary for the treatment period.
9. Dispense preservative free artificial tears (AT) eye drops to be administered 3 times daily.
10. Deliver instruction to Patient.
11. Dispense Patient Diary to record adherence to preservative free AT eye drops during the FU period, any new or changes in concomitant medications, any unusual medical conditions.

Visit 5 - Week 8 (day 56±2) FOLLOW-UP & END OF STUDY VISIT or EARLY EXIT VISIT*

1. Concomitant Ocular and Systemic Medications Update.
2. AEs monitoring (recording evaluation, as applicable).
3. Check the Patient's Diary of the Follow-Up period.
4. SANDE questionnaire.

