9.2 MONITORING AND REPORTING ADVERSE EVENTS

Following study informed consent form signature, at each visit, after the patient has had the opportunity to spontaneously mention any problems, the Investigator or appropriate designee should inquire about AEs by asking the standard questions:

- “Have you had any health problems since your last study visit?”
- “Have there been any changes in the medicines you take since your last study visit?”

AEs should be reported for any clinically relevant change in concomitant condition(s) that is the result of an untoward (unfavorable and unintended) change in patient's medical conditions. Changes in any protocol-specific ocular or systemic parameter evaluated during the study are to be reviewed by the Investigator. In addition, the patient's responses to any questionnaire utilized during the study are to be reviewed by the Investigator. Any untoward (unfavorable and unintended) change in a protocol-specific parameter or questionnaire response that is clinically relevant is to be reported as an AE. These clinically relevant changes will be reported regardless of causality.

All AEs should be followed-up to determine the outcome of the reaction.

In order to collect as complete as possible information in the clinical study database, all ADRs and SAEs ongoing at the time the subject's study participation ends should be evaluated within 10 days after the final visit. After this period, all unresolved ADRs and SAEs will be reported as "ongoing" in the eCRF.

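### The binding visit order puts adverse event questioning ahead of SANDE and investigator-scored staining; the exposure is mainly at Visit 4, and moving SANDE first is nearly free

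*Protocol*

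**What the plan says.** Protocol 8.1 and 8.2 carry the same instruction: "Site staff will conduct the following assessments in the order outlined below during each visit". The synopsis has an equivalent rule. In 8.2, Visits 4 and 5 begin with concomitant medication, AE monitoring and the diary check. SANDE follows, then a further questionnaire (redacted), then the eye examinations.

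Protocol 9.2 has the investigator or a designee ask at each visit, after the patient has had the chance to volunteer problems: "Have you had any health problems since your last study visit". It adds that "the patient's responses to any questionnaire utilized during the study are to be reviewed by the Investigator", so that clinically relevant unfavourable changes are reported as AEs. It does not say when in the visit this review takes place.

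Four other provisions bear on the point:
- Section 2.5 names eye and eyelid pain as the most common AEs with rhNGF. Section 6.2 gives rates from earlier dry eye trials: "48% patients reported eye pain in NGF0121 - PROTEGO-1, up to 63.5% in NGF0118, and 42% in NGF0216". No vehicle rates are given.
- Section 6.4.3 bases masking on appearance, packaging and labelling.
- Section 8.3 has the patient complete SANDE. Section 3.2.2 has the investigator score Week 4 staining.
- Section 4.1 allows only sponsor-supplied artificial tears between Visits 4 and 5.

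**The concern.** Matched vials cannot hide a sensation on instillation. Two paths follow from asking about AEs first. The patient may be reminded of eye pain, or of a guess about treatment, shortly before rating symptoms. The investigator may hear of pain shortly before giving a judgment-based staining score, and no separate masked assessor is named.

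At baseline every patient has been on vehicle, so any priming is the same in all arms. After randomization it differs wherever pain rates differ, and taking change from baseline does not remove it. At stake are staining at Week 4 (key secondary #3), Week 4 SANDE (a secondary endpoint) and, less directly, the primary analysis.

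**Working it through.** **1. Sequence and recall window (Protocol 8.1, 8.2, 9.2).**

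| Visit | AE step | Diary check before SANDE | SANDE | Staining | Period the AE question covers |
|---|---|---|---|---|---|
| 2 | item 2 | no | item 4 | 6.I | vehicle run-in, all patients |
| 4 | item 2 | item 3 | item 4 | 6.I | Visit 3 to Visit 4, on treatment |
| 5 | item 2 | item 3 | item 4 | 6.I | Visit 4 to Visit 5, off study drug |

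The diary checked at Visit 4 covers the treatment period; the one at Visit 5 covers follow-up.

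**2. Which endpoints are exposed.** At Visit 4 the question reaches on-treatment pain, and staining and SANDE follow. At Visit 5 it reaches such pain only if the pain persists or an earlier AE is being followed to outcome, as 9.2 requires. Schirmer-I is a wetted length in millimetres and leaves little room for expectation.

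**3. Route into the primary analysis.** Week 4 SANDE is a response in the mixed model and a variable in the imputation (SAP 8.1.1, Appendix 13.3). Each imputed dataset is complete and the treatment-by-visit terms are saturated. Week 4 values therefore reach the Week 8 contrast through imputed Week 8 values and, slightly, through the shared baseline slope. The influence is small when few data are missing.

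**4. The plan's sample size, to fix the standard error.** Inputs from Protocol 10.1: means −28.2 and −17.4 (difference 10.8), SDs 26.36 and 20.29, one-sided alpha 0.0125, power 80%.
- Normal formula: n = (2.241 + 0.842)² × (26.36² + 20.29²) / 10.8² = 9.505 × 1106.5 / 116.64 = 90.2, so 91 per group.
- The unequal-variance t calculation gives 92 (power 0.802), and 92 / 0.95 = 96.8, so 97. The plan's figures reproduce.
- Standard error of the difference at 92 per group: √(1106.5 / 92) = 3.47 points.

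**5. Scale of an assumed SANDE bias b.** The documents give neither its size nor its sign. If b favours the drug, type I error = 1 − Φ(2.241 − b/3.47). If b goes against it, power = Φ((10.8 − b)/3.47 − 2.241).

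| b (points) | Per-comparison type I error, bias for drug | Power at 10.8, bias against drug |
|---|---|---|
| 0 | 0.0125 | 0.81 |
| 1 | 0.025 | 0.72 |
| 2 | 0.048 | 0.62 |
| 3 | 0.084 | 0.50 |
| 4 | 0.138 | 0.39 |

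No such table can be made for staining, because the documents give no SD for it.

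**6. How informative a pain report is.** With 1:1:1 allocation, P(active given pain) = (2/3)a / [(2/3)a + (1/3)v], for active rate a (taken as equal in both active arms) and vehicle rate v. The vehicle rates, and the 20% active rate, are assumptions.
- a = 20%, v = 20%: 67%, which is no information.
- a = 20%, v = 10%: 80%.
- a = 42%, v = 10%: 89%.
- a = 48%, v = 5%: 95%.

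This describes a pain report taken at any point in the visit. It does not measure what the order adds.

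**The case against.** The case on the other side has real force.

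- **The primary endpoint.** A reader might infer that the drug's eye pain is raised just before the primary SANDE rating. The documents do not support that: the Visit 5 question and diary cover weeks on artificial tears only. This objection stands, apart from persisting or followed-up events and any belief carried forward from Visit 4.
- **Same order in all arms and at baseline.** This is true, but it protects only if pain rates are equal across arms. They may be closer than in earlier trials, since the protocol seeks better tolerability.
- **Patients already know.** They instil the drops three times a day, so reordering cannot restore masking of a sensation. This stands; the fix removes only the prompt.
- **Direction.** A reminder of pain could worsen SANDE on active drug and work against superiority, while a guess of active treatment could improve it. Neither is established.
- **The rater.** A designee may take the AE history, and Visit 3 knowledge persists in any case. Both are true, but nothing requires that the person scoring staining be someone else.
- **Visit 1 as a model.** A reader might cite its closing AE step as the better order. It is a poor comparator: that step follows the first drop of study product, and medications are reviewed before SANDE there too.
- **Asking about AEs last.** Questioning after Schirmer strips and dyes may elicit procedure-related ocular symptoms in a trial with a tolerability objective. The documents state no reason for the present order, so this is inference, but it is a fair argument against moving all AE questioning to the end.

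**Conclusion.** The concern holds in limited form. The order is binding, and it places AE questioning before SANDE and before investigator-scored staining. It is strongest at Visit 4, for key secondary #3 and Week 4 SANDE. For the primary endpoint the path is indirect.

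Any bias requires pain rates to differ between arms. For staining it also requires that the report reach the scorer. The documents establish neither, so the figures in steps 5 and 6 are scale and not estimates. They do not support a claim that the primary result is biased or that the masking has failed. The change is worth making because it costs almost nothing and closes a path that can differ by arm after randomization.

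**What to change.** In Protocol 8.1, 8.2 and the synopsis:

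1. Make SANDE the first step at Visits 2, 4 and 5, before concomitant-medication, AE and diary review. Including Visit 2 keeps baseline and follow-up in the same order.
2. In 9.2, state that the investigator reviews questionnaire answers for AEs only after staining has been recorded.
3. Where existing staffing allows, have the designee already permitted in 9.2 take the AE history, rather than the person who scores staining.
4. Do not require all AE questioning to follow the Schirmer and dye procedures.
5. Reconcile Visit 4: the synopsis has a closing AE step (item 12) that 8.2 lacks.

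No procedure is added, and sample size, alpha and power are unchanged. Patients already enrolled (18 at Amendment 2, more if the change comes later) will have used the present order. Anyone mid-study could have different orders at baseline and follow-up. Knowledge from the Visit 3 AE check remains.
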